## Objectives

List your research objectives. Please include a summary of intended research objectives in the box below.

### Hypothesis and Aims:

Moringa leaf supplementation in porridge and placebo in porridge will be acceptable to lactating mothers and 6-59 month old children. Three months of high dose Moringa leaf supplementation to breastfeeding mothers of neonates in Kisumu, Kenya will lead to improved infant growth and nutrition compared to controls.

Aim 1: Determine acceptability, composition, and preference of consumption of moringa and placebo in porridge.

Aim 2: Test the hypothesis that three months of daily moringa leaf supplementation to breastfeeding mothers for infants and to children 6-59 months for themselves will improve childhood growth and nutritional status via measurements of growth, Vitamin A, and iron deficiency.

Aim 3: Assess mechanisms of improved infant and childhood growth and nutritional status as defined by 1) improved intestinal health using biomarkers of Environmental Enteric Dysfunction and prevalence of diarrhea, and 2) improved breastmilk volume and composition.

## Study Design

Describe and explain the study design (e.g., observational, secondary analysis, single/double blind, parallel, crossover, deception, etc.).

- **Clinical Research:** Indicate whether subjects will be randomized and whether subjects will receive any placebo.
- **Community-Based Participatory Research:** If you are conducting [community-based participatory research \(CBPR\)](#), describe strategies for involvement of community members in the design and implementation of the study, and dissemination of results from the study.
- **Qualitative research:** Indicate ranges where flexibility is needed, if a fixed interview transcript is not available, describe interview topics including the most sensitive potential questions.
- **Research Repositories:** If the purpose of this submission is to establish a Research Repository (bank, registry) and the material you plan to collect is already available from a commercial supplier, clinical lab, or established IRB approved research repository, provide scientific justification for establishing an additional repository collecting duplicate material. Describe the repository design and operating procedures. For relevant information to include, see the [UK Research Biospecimen Bank Guidance](#) or the [UK Research Registry Guidance](#).

### We will implement:

A) a short acceptability study of acceptability, adherence, and preference for moringa dried leaf consumption and placebo consumption in porridge. Selection will be from lactating women 18 years and over and children 6-59 months; subjects will come from our target region of Kisumu.

B) a pilot placebo-controlled RCT of mother-infant dyads and their children 6-59 months who present for first postnatal check to two high volume rural maternal and child health centers in Kisumu, Kenya.

Inclusion criteria: lactating women of at least 18 years of age and their exclusively breastfed infants within 30 days of delivery with informed consent. Children 6-59 months of age who are eating food.

Exclusion criteria: regular maternal consumption of moringa, receipt and consumption of food supplementation program, or inability to feed orally; for infant, significant congenital disease, inability to feed orally. For mother or child: inability to orally feed or complete refusal (>3 days) to eat moringa or placebo porridge.

Sample size: 100 infant-mother pairs in each arm (n=400 participants total). 100 children in each arm (n=200)

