**Phase B) Pilot RCT**

Inclusion criteria: lactating women of at least 18 years of age and their exclusively breastfed infants within 30 days of delivery with informed consent. Children 6-59 months who are orally feeding with caregiver informed consent.

Exclusion criteria: regular maternal consumption of moringa in the month prior to study enrollment, receipt and consumption of food supplementation program, or inability to feed orally; for infant, significant congenital disease, inability to feed orally. For child: inability to feed orally or refusal to eat porridge (>3 days consecutively).

We anticipate enrolling up to 50 mother-infant dyads in each of two arms and 50 children in each of two arms.

We propose starting enrollment as soon as all ethical approvals obtained, personnel hired, and study supplies obtained; there is no additional sample composition of subjects. This study targets women and infants as breastfeeding infants have the potential to receive the greatest benefit from moringa leaf supplementation to their lactating mothers.

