**Not involve greater than minimal risk.**

In the Risk Level section of the IRB Application you indicated your research does not involve greater than minimal risk.

A. Explain why your research does not involve greater than minimal risk:

Risks are: discomfort and bleeding or bruising from capillary stick. Infants and children receive this as a routine physical test in their lifetimes. This is a routine test for newborn screening at birth and again for blood sugar checks if blood sugars are low and again for hemoglobin assessment between 12-24 months of age.

Additional risks are bloating and/or diarrhea from the consumption of moringa or the placebo; both contain a lot of soluble fiber.

Additional risks are not liking the taste of moringa or placebo.

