### Intervention:

Mothers: 20g moringa leaf powder vs. placebo in the staple food of porridge consumed daily for three months. Children: 10g moringa leaf powder vs. placebo in porridge consumed daily for three months. Moringa dose will be determined by the upper limit of acceptability in Phase A.

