### Phase B)

Participants regularly receive postnatal appointments at their health center for routine child check with health center staff. During this visit, our trained study personnel will enroll the participants and separately perform anthropometrics (weight, height or length, mid upper-arm circumference), collect blood, fecal, and breastmilk sample, and distribute study supplies. At monthly visits (month 1, 2, exit visit at month 3), followup will occur at the participant's study site. At these visits, study staff will perform anthropometrics, review porridge and/or moringa consumed, review parental diary, distribute study supplies, and at end visit will again collect blood, fecal, and breastmilk samples as applicable. Compliance with porridge-moringa ratio will be assessed by review of parent recorded amount consumed in the diary and direct visualization of percentage of porridge and leaf powder remaining prior to distribution. This will occur via verbal recall for parents identifying as illiterate.

Biological samples of mothers, infants and children (blood by heel stick or finger stick and stool) will be collected by trained study personnel at the presenting health center on enrollment and exit (3 months). Hemoglobin will be assessed by Hemoccue® utilizing a capillary (heel or finger) stick with direct readout. Capillary blood by heel or finger stick will be transferred to special paper and dried appropriately to create Dried Blood Spots by a standardized process and/or stored in aliquot containers. Fecal collection will occur on the day of monthly presentation to the health center, or kits and instructions will be given to caregivers and the stool collected by study personnel in the participant's village. Hemoglobin will be recorded to the nearest 0.1 g/dL by Hemoccue®. Stool, breastmilk, and blood samples will be immediately chilled and transported to Kenya Medical Research Institute Lab (KEMRI) in Kisumu, processed, and stored at -80 degree C freezers until transport. Samples will then be shipped on dry ice to the University of Kentucky or to the contracted laboratory for analysis. Breastmilk will be transported to Eurofin Laboratories or the laboratory of analysis. Breastmilk volume will be performed at enrollment and exit by 24 hour breastmilk volume pumped by hand pump that we supply and measured with the milk subsequently fed to the infant.

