## Statistical Analysis Plan – 58219

Statistical Analysis: Data analyses were performed using SPSS v28 (IBM Corp. 2021) with graphing via SPSS and Prism GraphPad (v9.5.1). Using an intention-to-treat approach, we performed univariate and multivariable analysis for primary and secondary outcomes as change from baseline per individual/group and between groups. We used Pearson's (for normally distributed data) or Spearman's (for non-normally distributed data) correlation to examine relationships between continuous variables, Pearson's chi square and Fisher's exact tests between categorical variables, and independent t-test or Mann-Whitney U test between binary and continuous variables as appropriate. Paired samples t-tests or Wilcoxon matched-paired sign-rank test were used for paired data. Continuous variables are presented here as mean with standard deviation (if normally distributed) as mean  $\pm$  SD or median with interquartile range (if not normally distributed) as median, IQR, while categorical variables are presented with counts and percentages. An alpha-level of 0.05 was used to determine significance. All enrolled participants who continued study activities through at least the first month were analyzed regardless of loss to follow up.

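### The Study Design exclusion for refusing the study porridges conflicts with the Subject Demographics rule, can in practice be met only after supplies are handed out, and so can bias the arm comparison

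*Combined protocol and SAP*

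**What the plan says.** The protocol states the Phase B porridge exclusion twice.

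- Study Design, under the pilot RCT: "For mother or child: inability to orally feed or complete refusal (>3 days) to eat moringa or placebo porridge".
- Subject Demographics, Phase B: "For child: inability to feed orally or refusal to eat porridge (>3 days consecutively".

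Under Research Procedures, Phase B, the visit at which staff enrol participants is also the one at which they "collect blood, fecal, and breastmilk sample, and distribute study supplies". On dose, the Intervention paragraph says: "Moringa dose will be determined by the upper limit of acceptability in Phase A". The risk section for children lists taste: "Additional risks are not liking the taste of moringa or placebo".

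The SAP describes its analysis as "Using an intention-to-treat approach" and then defines the set analysed: "All enrolled participants who continued study activities through at least the first month were analyzed regardless of loss to follow up".

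**The concern.** An eligibility criterion should describe people before they are allocated. The Study Design version names the two trial products, so it turns on how a participant responds to the porridge received. If people are taken out for that reason, those left in each arm are those who tolerated that arm's product, and randomisation no longer protects the comparison.

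Refusal that differs by arm is plausible because the moringa dose is tied to the upper end of what Phase A participants accept. A refusing mother matters for the infant comparison too: she is enrolled as half of a pair, and the infant's growth is the outcome. Refusal is also something a pilot of a food supplement should report, not remove through eligibility.

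**Working it through.** **1. The two rules side by side**

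| | Study Design | Subject Demographics, Phase B |
|---|---|---|
| Who | mother or child | child only |
| What is refused | moringa or placebo porridge | porridge, unspecified |
| Degree | complete refusal | refusal |
| Duration | >3 days | >3 days, consecutive |

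A mother who refuses the study porridge is excluded under the first rule and kept under the second.

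**2. When the Study Design rule can be met.** Supplies are distributed at the enrolment visit. No Phase B tasting or run-in is described. Phase A tasting cannot serve as the screen: it is a separate sample of about 10 adults and 10 children recruited through community groups, whereas Phase B recruits at health centres. More than three days of refusing study porridge can therefore be seen only after supplies are received.

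**3. What the SAP does with such a person.** An excluded participant who stops in the first weeks has not continued through month 1 and is not analysed. One who refuses but continues past month 1 is analysed. The SAP does not define which study activities count as continuing.

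**4. Size on a continuous outcome.** The documents give no refusal rate and no outcome figure for refusers, so every rate here is an assumption. Assume no true effect and the same deficit d (acceptors minus refusers) in both arms. Removing a fraction r raises an arm's mean by r × d, so the bias is (r_moringa − r_placebo) × d.

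| Removed, moringa vs placebo | Difference | d = 0.3 SD | d = 0.5 SD |
|---|---|---|---|
| 10% vs 2% | 0.08 | 0.024 | 0.040 |
| 20% vs 5% | 0.15 | 0.045 | 0.075 |
| 30% vs 5% | 0.25 | 0.075 | 0.125 |

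At 50 per arm the standard error of a standardised difference is √(2/50) = 0.20 SD. The largest case is therefore 0.125/0.20, about 0.6 standard errors. Two-sided type I error would be about 0.055, 0.066 and 0.096 at biases of 0.04, 0.075 and 0.125 SD, ignoring the smaller numbers retained.

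**5. Size on stunting.** Take the protocol's 25% prevalence in both arms and no true effect. If refusers have risk q, the retained risk is (0.25 − r × q)/(1 − r).

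| Removed, moringa vs placebo | q | Moringa retained | Placebo retained | Apparent benefit, points |
|---|---|---|---|---|
| 10% vs 0% | 50% | (0.25 − 0.05)/0.90 = 22.2% | 25.0% | +2.8 |
| 20% vs 5% | 50% | (0.25 − 0.10)/0.80 = 18.8% | (0.25 − 0.025)/0.95 = 23.7% | +4.9 |
| 20% vs 0% | 50% | 18.8% | 25.0% | +6.3 |
| 20% vs 0% | 10% | (0.25 − 0.02)/0.80 = 28.8% | 25.0% | −3.8 |
| 10% vs 10% | 50% | 22.2% | 22.2% | 0 |

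The SAP says "An alpha-level of 0.05 was used to determine significance" without stating sidedness; two-sided is assumed here. In the +6.3-point case, type I error is about 0.11 at 50 per arm (the size under Subject Demographics) and 0.17 at 100 per arm (the size under Study Design).

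**The case against.** Removal after allocation is an inference. No section says when randomisation takes place, that refusers are withdrawn, or that their follow-up stops. A timeline table is listed as an attachment but is not in the public document. This stands, and it limits the claim to what the rule permits.

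The SAP has no exclusion for refusal or ineligibility, and it analyses a refuser who continues past month 1. A reader might infer that the criterion removes people from the analysis at any point in the three months. The SAP does not support that; the documented route is loss before month 1.

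A reader might also infer that the bias favours moringa. That needs both more refusal on moringa and worse outcomes in refusers. The risk section lists dislike of either product alike, so it shows no difference between arms. For the pairs, carrying the mother's refusal over to a deficit in her infant is a further unsupported step. The larger figures need 20 to 30% complete refusal, while the Background reports a positive local attitude to eating the leaf powder.

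Non-acceptance is not simply hidden either. Aim 1 addresses acceptability, a diary records daily consumption, and leftovers are inspected at visits. What is missing is a statement that refusal will be reported by arm.

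Finally, the Subject Demographics wording is neutral between arms and can be read as a check on ordinary porridge. It need not be deleted.

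None of this removes the contradiction between the two rules, or the fact that one of them conditions on response to a trial product.

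**Conclusion.** The concern holds as a defect in the rule as written. The two sections contradict each other, and the Study Design version can in practice be met only once study porridge is in hand. Following it can take early refusers out of the comparison. The intention-to-treat statement does not cure this, because the SAP's own analysis set requires continuation through month 1.

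The documents do not establish that anyone was excluded this way, or which arm would gain. Under the assumed rates the distortion runs from about 0.02 to 0.13 SD, or from −3.8 to +6.3 points in stunting. The SD range takes more refusal on moringa and worse outcomes in refusers as given. The sign reverses if refusers are at lower risk, and the bias is zero when refusal rates and refuser risk are equal across arms. For most of the assumed rates the effect on type I error is modest, but it cannot be judged unless refusals are reported.

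**What to change.** - Remove refusal of the moringa or placebo porridge from the Study Design exclusions and reconcile the two sections.
- If a porridge criterion is kept, as under Subject Demographics, state that it is an arm-neutral check on ordinary porridge, applied before randomisation only.
- State when randomisation takes place relative to enrolment and the first supplies.
- Record refusal after allocation as non-adherence and report it by arm, from the diary and leftover checks already planned.
- Keep every randomised participant in the planned measurements and analyse them in the assigned arm. In the SAP, replace the month-1 condition so that the analysis set matches the stated approach.
- The SAP is in the past tense and a later measurement of already consented infants is described, so enrolment may be complete. In that case, report the number excluded for refusal by arm and include them in the analysis wherever data exist.

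The cost is wording in the two protocol sections and the SAP, and perhaps one screening question, since the visits and consumption records already exist. The downside is that the estimated effect may be slightly diluted by participants who did not eat the porridge.

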### Intervention:

Mothers: 20g moringa leaf powder vs. placebo in the staple food of porridge consumed daily for three months. Children: 10g moringa leaf powder vs. placebo in porridge consumed daily for three months. Moringa dose will be determined by the upper limit of acceptability in Phase A.

### Data collection:

Monthly anthropometrics for mother, infant, and child. These include infant weight, length and maternal and child weight, height/length, and mid-upper arm circumference.

Enrollment and exit quantitative surveys including but not limited to Food Frequency Questionnaire from which we will calculate Dietary

Diversity Score.

Mother, infant and child finger or finger/ heel stick for hemoglobin and capillary blood collection at study enrollment and exit.

Mother, infant and child feces collection at study enrollment and exit.

Daily recording by parent in provided diary of daily moringa percent consumption, incidence of diarrhea, diagnosis by health professional of medical condition in mother, infant, or child.

Lactating Women:

24 hour volume of breastmilk at study enrollment and exit

Breastmilk sample collection (est. 5ml) at study enrollment and exit

We would like to complete one more anthropometric measurement (weight and length) of enrolled infants in the next few months; this is 8-12 months from study start.

#### Attachments

#### Subject Recruitment Methods & Advertising

Describe how the study team will identify and recruit subjects. Please consider the following items and provide additional information as needed so that the IRB can follow each step of the recruitment process.

- How will the study team identify potential participants?
- Who will first contact the potential subjects, and how?
- Will you use advertisements? If so, how will you distribute those?
- How and where will the research team meet with potential participants?
- If applicable, describe proposed outreach programs for recruiting women, minorities, or disparate populations.
- How will minimize undue influence in recruitment?
- Attach copies of all recruiting and advertising materials (emails, verbal scripts, flyers, posts, messages, etc.).

For additional information on recruiting and advertising:

- [IRB Application Instructions - Advertisements](#)
- [PI Guide to Identification and Recruitment of Human Subjects for Research](#)

#### Phase A)

We will recruit adults and children from communities in the population of Pamoja Community Based Organization.

#### Phase B)

We will recruit mothers and their infants and children 6-59 months at two regional health centers. At the regional health center, mothers arrive for their postnatal visits with their babies and for well child checks. With regional health center approval, study personnel will approach potentially eligible mothers and provide face-to-face informed consent by written and verbal means. The study personnel will speak in the mother's language (English, Swahili, or Luo). Mother will provide consent for herself and her eligible infant and child. The study personnel will clearly communicate that we are not her medical care team, and that the potential study participant may choose not to enroll and that this will not affect her or her infant or child's medical care in any way.

no advertising

#### Attachments

## Research Procedures

Describe how the research will be conducted.

- What experience will study participants have?
- What will study participants be expected to do?
- How long will the study last?
- Outline the schedule and timing of study procedures.
- Provide visit-by-visit listing of all procedures that will take place.
- Identify all procedures that will be carried out with each group of participants.
- Describe deception and debrief procedures if deception is involved.

Differentiate between procedures that involve standard/routine clinical care and those that will be performed specifically for this research project. List medications that are explicitly forbidden or permitted during study participation.

### Phase A)

Participants will be offered unlabelled variations of porridge with moringa and/or with placebo. Participants will eat the portion. Utilizing standard questionnaires, participants will verbally or by writing rate their preferences and opinions of these variations in regards to acceptability, palatability, and adherence of each variation of porridge.

### Phase B)

Participants regularly receive postnatal appointments at their health center for routine child check with health center staff. During this visit, our trained study personnel will enroll the participants and separately perform anthropometrics (weight, height or length, mid upper-arm circumference), collect blood, fecal, and breastmilk sample, and distribute study supplies. At monthly visits (month 1, 2, exit visit at month 3), followup will occur at the participant's study site. At these visits, study staff will perform anthropometrics, review porridge and/or moringa consumed, review parental diary, distribute study supplies, and at end visit will again collect blood, fecal, and breastmilk samples as applicable. Compliance with porridge-moringa ratio will be assessed by review of parent recorded amount consumed in the diary and direct visualization of percentage of porridge and leaf powder remaining prior to distribution. This will occur via verbal recall for parents identifying as illiterate.

Biological samples of mothers, infants and children (blood by heel stick or finger stick and stool) will be collected by trained study personnel at the presenting health center on enrollment and exit (3 months). Hemoglobin will be assessed by Hemoccue® utilizing a capillary (heel or finger) stick with direct readout. Capillary blood by heel or finger stick will be transferred to special paper and dried appropriately to create Dried Blood Spots by a standardized process and/or stored in aliquot containers. Fecal collection will occur on the day of monthly presentation to the health center, or kits and instructions will be given to caregivers and the stool collected by study personnel in the participant's village. Hemoglobin will be recorded to the nearest 0.1 g/dL by Hemoccue®. Stool, breastmilk, and blood samples will be immediately chilled and transported to Kenya Medical Research Institute Lab (KEMRI) in Kisumu, processed, and stored at -80 degree C freezers until transport. Samples will then be shipped on dry ice to the University of Kentucky or to the contracted laboratory for analysis. Breastmilk will be transported to Eurofin Laboratories or the laboratory of analysis. Breastmilk volume will be performed at enrollment and exit by 24 hour breastmilk volume pumped by hand pump that we supply and measured with the milk subsequently fed to the infant.

We would like to complete one more anthropometric measurement (weight and length) of enrolled infants in the next few months; this is 8-12 months from study start. This would entail calling previously consented participants, asking them to come to the sub-county hospital, ensuring they agree to and sign the modified informed consent, and performing length and weight in the same method as previously and recording this is Redcap as previously done. We would provide the reimbursement of 500 Kenyan shillings, ~5USD.

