**Aim 3: Assess mechanisms of improved infant or child growth and nutritional status as defined by improved infant intestinal health using biomarkers of Environmental Enteric Dysfunction and prevalence of diarrhea**

Sample collection: Baseline and exit visit collection of stool samples, prevalence of diarrhea

Intestinal health measurements: Markers of environmental enteric dysfunction (fecal neopterin, myeloperoxidase, alpha-1- antitrypsin), and prevalence of maternal and infant acute diarrheal illness (>3 watery stools in 24 hours). The rationale for this choice of biomarkers comes from the largest study of markers of environmental enteric dysfunction to date, the MAL-ED cohort, that determined that fecal neopterin, myeloperoxidase, and alpha-1-antitrypsin provide the most sensitive measures of intestinal inflammation and integrity in breastfeeding infants.(50,51) MAL-ED additionally established improved performance of these fecal markers over the previous standard of urine lactulose:mannitol ratio to assess intestinal integrity. These assays will be completed at the UK Biomarker Analysis Laboratory with send-out as needed to UK approved facilities. The impact on intestinal health may also be visible in mothers directly consuming moringa. For this reason, we are collecting maternal stool and analyzing it for the same markers of EED as well as for fecal calprotectin as a measure of intestinal inflammation. In addition to more directly quantifying moringa's impact on intestinal health, increased maternal intestinal integrity may lead to improved nutrition and impact her breastmilk quality or quantity.

**Aim 3: Assess mechanisms of improved infant growth and nutritional status of infants as defined by improved breastmilk volume and composition including Vitamin A precursors and antioxidants.**

Sample collection: At exit, maternal breastmilk.

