Breastmilk measurements: Volume (24 hour pre and post-breastfeeding infant weights), vitamin A and its precursors (retinols), antioxidants (catalase, Vitamin E, lactoferrin), and nutritional profile (fatty acid profile and protein analysis). Measures of breastmilk volume include assessment of 24 hour breast pumping or hand expression or weighing the infant before and after feeding for 24 hours.(52–56). Breastmilk contains a wide variety of nutrients necessary for growth and multiple bioactive compounds that can dramatically affect infant health by modifying inflammation. Breastmilk components vary according to time from birth as well as maternal nutritional status, dietary intake, and disease states. Compounds that act to modify inflammation include vitamins and their precursors such as Vitamin A, retinols, and Vitamin E, as well as catalase, lactoferrin, and certain fatty acids.(57–59) All assays will be completed in Eurofin Laboratories. Due to the likelihood of moringa to improve any pre-existing maternal vitamin A or iron deficiency and this, in turn, affecting the composition of breastmilk (most notably in vitamin A precursors), we will also collect maternal blood for vitamin analysis.

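### Two sections define 24-hour breastmilk volume by different methods, and none fixes one method for every woman at both visits

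*Combined protocol and SAP*

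**What the plan says.** **Volume.** Study Design (Data collection) asks for "24 hour volume of breastmilk at study enrollment and exit" and names no method. Research Procedures, Phase B, names one: "Breastmilk volume will be performed at enrollment and exit by 24 hour breastmilk volume pumped by hand pump that we supply", the milk being "measured with the milk subsequently fed to the infant". Data Collection & Research Materials, under Aim 3, begins its measurement list differently: "Breastmilk measurements: Volume (24 hour pre and post-breastfeeding infant weights". The sentence after that list gives pumping, hand expression or weighing the infant around feeds as measures of volume, with citations, and selects none of them.

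**Milk samples.** Study Design has a sample taken at enrolment and at exit. Phase B agrees: at enrolment, staff "collect blood, fecal, and breastmilk sample, and distribute study supplies", and "at end visit will again collect blood, fecal, and breastmilk samples as applicable". The Aim 3 breastmilk text says "Sample collection: At exit, maternal breastmilk". The Aim 3 stool line in the same section names both times: "Baseline and exit visit collection of stool samples, prevalence of diarrhea".

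**Analysis.** The SAP analyses primary and secondary outcomes as change from baseline, by univariate and multivariable methods. It does not say which outcomes these are, lists no covariates, and does not mention breastmilk.

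**The concern.** Hand pumping records how much milk a woman expresses in 24 hours. Weighing the infant before and after breastfeeds records how much the infant takes from the breast. Milk that is pumped off and fed later is not captured by weights around a breastfeed, so the same feeds cannot supply both measurements. A reader of the plan cannot tell which quantity the word volume will denote in the results.

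What is at stake is the interpretation of a mechanism. The hypothesis is that moringa works partly by raising milk volume. If some women were pumped and others weighed, an arm comparison would average two different quantities. If a woman's method changed between visits, her change would mix a method difference with any real change.

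The exit-only line raises a smaller question. If it were followed, composition would have no enrolment value, and neither change from baseline nor adjustment for enrolment would be possible. A between-arm comparison at exit would remain.

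**Working it through.** The plan gives no figure on this point to reproduce. The first three steps compare text; only the last uses arithmetic.

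**1. Volume, place by place**

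| Place | Method | Time |
|---|---|---|
| Study Design, Data collection | none named | enrolment and exit |
| Research Procedures, Phase B | hand pump, milk then fed to infant | enrolment and exit |
| Data Collection & Research Materials, Aim 3, definition | infant weights around breastfeeds | not stated |
| Same place, next sentence | pumping, hand expression or weighing; no choice | not stated |
| SAP | not mentioned | not mentioned |

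The timing of volume is consistent wherever it is given. The method is not. No row contains a rule for choosing, a conversion between methods, or a requirement that every woman be measured in the same way at both visits.

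**2. Milk samples**

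Study Design says enrolment and exit. Phase B describes collection at the enrolment visit and again at the end visit. One Aim 3 line says exit. That is one line against three statements. The stool line shows that the section does name baseline when it means it, so the omission should be corrected rather than ignored.

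**3. Does the SAP settle either point?**

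No. It names no outcome, so its change-from-baseline rule covers milk only if milk is among the unnamed secondary outcomes.

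**4. What the choice of analysis costs once both values exist**

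Let S be the standard deviation at each visit (assumed equal) and r the enrolment-exit correlation (assumed; the documents give none).

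- SD of the change score: S × √(2(1 − r))
- Residual SD of the exit value adjusted for enrolment: S × √(1 − r²)

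At a fixed sample size, alpha and power, the detectable difference is proportional to these SDs. The ratio of unadjusted change to adjusted analysis is therefore √(2(1 − r)) / √(1 − r²) = √(2 / (1 + r)), whatever the number of dyads.

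| r | Change SD / S | Adjusted SD / S | Ratio | Extra difference needed |
|---|---|---|---|---|
| 0.3 | √1.40 = 1.183 | √0.91 = 0.954 | 1.240 | 24% |
| 0.5 | √1.00 = 1.000 | √0.75 = 0.866 | 1.155 | 15% |
| 0.7 | √0.60 = 0.775 | √0.51 = 0.714 | 1.085 | 8% |

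The ratio applies to a t-test of change; the Mann-Whitney case was not calculated.

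Adjusting a model of change gives the same arm effect as adjusting a model of the exit value. If (exit − enrolment) = a + b × arm + c × enrolment, then exit = a + b × arm + (1 + c) × enrolment, and b is unchanged.

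**The case against.** The best defence is that the sections play different roles. Phase B is the operating procedure: it names one method, supplies the pump, gives the times and says what happens to the milk. The Aim 3 text can be read as a survey of available methods, since its second sentence admits pumping, and no section describes how 24-hour weighing would be carried out. On that reading everyone is pumped and only a label is wrong. This largely stands as a guess at intent. It does not remove the conflict, because the definition at the head of the Aim 3 list still names weighing alone, and the sentence that admits pumping leaves the choice open.

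Three stronger inferences are tempting, and the documents do not support them:

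- **That methods were mixed across women, arms or visits.** No section says so. The plan merely fails to rule it out.
- **That no enrolment milk was planned.** Study Design and Phase B both provide for it explicitly.
- **That the SAP uses only unadjusted change.** It also names multivariable analysis of change. If the enrolment value is among the covariates, the arm effect already equals that of the adjusted exit analysis. The covariates are simply not listed.

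It is also fair to say that two attachments listed under Data Collection & Research Materials, a timeline and outcome table and a data collection workbook, are not reproduced and may show what was intended. The three sections would still need to agree with them.

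**Conclusion.** The plan contradicts itself on how 24-hour breastmilk volume is measured: expressed yield in Research Procedures, infant intake in the Aim 3 definition, and an unresolved list directly after it. Nothing fixes one method for every woman at both visits. That the two methods measure different quantities is a methodological judgement, resting on what each one physically records. The size of the discrepancy cannot be derived from the documents, and none is claimed.

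The exit-only sampling line is a minor inconsistency and probably a slip.

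The only quantified part is the analysis: an unadjusted change score needs a true difference 8% to 24% larger than a comparison adjusted for the enrolment value. This assumes correlations from 0.7 down to 0.3 and equal variance at the two visits, and the penalty disappears if the SAP's multivariable model already includes the enrolment value.

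The point affects the reading of a mechanistic outcome in a pilot. It does not bear on the growth comparison. It is worth correcting because the correction is easy.

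**What to change.** **Protocol.** Make Phase B and the Aim 3 breastmilk measurement text name the same volume method, and state that it is used for every woman at both visits. Correct the Aim 3 sampling line to enrolment and exit. Check both against the two attachments.

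**SAP.** List 24-hour volume and each composition measure as outcomes. Compare arms with the enrolment value as a covariate, on either the exit value or the change, in place of an unadjusted t-test or Mann-Whitney test of change. Report by arm how many women have an enrolment value and how many have an exit value.

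**If data are already collected.** The SAP is written in the past tense, so this may apply. State the volume method and sampling times actually used. If methods were mixed, report volume by method, and do not read a woman's change as a change in volume if her method switched. If only exit milk exists, present composition as a between-arm comparison at exit.

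**Cost.** Wording edits in the protocol and two or three lines in the SAP. No visit or procedure is added, since collection at enrolment and exit is already planned. After data collection, the cost is a statement of what was done.
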